Study Title: A More Physiological Feeding Process in ICU:the Intermittent Infusion With Semi-solidification of nutrients

ClinicalTrails.gov ID: NCT 03017079

Date: 11/24/2016

Responsible party: [name]

Email: [contact]

Study Protocol

一. Purpose

- 1) To investigate whether intermittent feeding with semi-solid nutrients improves the enteral nutrition complications of diarrhea, reflux and aspiration;
- 2) Observe the feeding intolerance and the efficiency of the EN of critically ill patients;
- 3) Observe the blood sugar and insulin secretion;

二. Design and method

(1) Single center, randomized, single blind, controlled prospective study;

(2) Inclusion criteria:

- 1) not less than 14 years old of critical illnesses;
- 2) No long-term history of oral administration of gastrointestinal motility drugs;
- 3) Nasogastric tube for enteral nutritional support treatment;
- 4) No acute pulmonary infection;
- 5) No previous history of upper gastrointestinal surgery;

(3) exclusion criteria:

- 1) Refuse into the study;
- 2) Stay in ICU less than 3 days
- 3) acute pulmonary infection before entering the ICU;
- 4) have nutritional contraindications, such as intestinal ischemia or obstruction, gastrointestinal hemorrhage and so on;
- 5) No enteral nutrition received for less than 3 days;

(4) Abort criteria:

- 1) Abandoning treatment and discharge, resulting in incomplete data
- 2) EN contraindications nutrition during treatment;
- 3) Other condition of researchers think that patients are not fit to continue with the study;

(5) Groups

[figure not shown]
- 1) intermittent feeding (IF)
- 2) intermittent feeding with semi-solid nutrients (IS)

If you are assigned to the IS group, you should first receive a package of semi-solid agent to increase the intestinal nutrition viscosity. If you are assigned to the IF group, you will receive the routine nutrition treatment, and the treatment time for both groups is 3 days. After 3 days, you will receive routine enteral nutrition therapy. If there were serious enteral nutrition complications such as aspiration and abdominal distension within 3 days, the experiment would end. The treatment of the two groups only depends on whether semi-solid agent was added, while the rest of the treatment measures were consistent.

(6) Test

Blood (Microvascular blood sugar+ C-peptide release test), Secretions from the posterior pharynx and trachea;

三. Study process

四. How to protect high-risk groups or vulnerable groups

The subject of this study is critically illnesses. Before entering the research group, the researchers must obtain the informed consent by the patient or the agent authorizer about the specific content of the study. For details, please refer to the informed consent.

五. Sample Size Calculating

According to the literature reported, the incidence of gastrointestinal intolerance (FI) is about 30.8%. We presume that $\delta = -0.05$, $\alpha = 0.025$, $\beta = 0.20$, the non-inferior efficiency test design is

$$(n_1 = n_2 = \frac{(Z_{1-\alpha/2} + Z_{1-\beta})^2 [\pi_1(1-\pi_1) + \pi_2(1-\pi_2)]}{(\pi_1 - \pi_2 - \delta)^2})$$

adopted and the formula is applied:

六. Data management and confidentiality

Data entry and management were designed in the form of a case report. A case report is a document designed according to the protocol for recording the data of each subject during the

trial.

All records relating to the subject's identity shall be kept confidential and shall not be made public to the extent permitted by applicable laws and/or regulations.

七. Informed consent

The subject of this study is critically illnesses. Before entering the research group, the researchers must obtain the informed consent by the patient or the agent authorizer about the specific content of the study. For details, please refer to the informed consent. The specific procedures for obtaining informed consent include oral and written informed consent from the physician to the patient, patient's family or authorized agent for the above study. The patient volunteered to participate in the study. Patients understand that they can withdraw from the study at any time for no reason, without affecting their future treatment. At the same time, the patient or the agent authorizer will obtain a copy of this informed consent. At the same time, the subjects included in this study were critically illnesses, and the subjects, told and signed, were mainly immediate family members.

八. Report of adverse events

After entering this study, there were some possible adverse reactions:

- (1) Diarrhea, which is most popular, may cause water and electrolyte disturbance in severe cases;
- (2) Nausea and vomiting, and stomach retention;
- (3) High and low blood sugar;
- (4) Aspiration is one of the more serious complications. Patients with weakness, old age or coma are more likely to have liquid diet reflux, especially those with esophageal reflux.
- (5) Take off and plug the pipe.

Patients will not receive additional treatment or take additional risks for participating in the study

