Study Title: A More Physiological Feeding Process in ICU:the Intermittent Infusion With Semi-solidification of nutrients

ClinicalTrails.gov ID: NCT 03017079

Date: 11/24/2016

Responsible party: [name]

Email: [contact]

Statistical Analysis Plan

Data were expressed as means \pm standard deviations (SD) for quantitative variables and proportions for categorical and binary variables. Student's t test was used for statistical comparison between groups for continuous variables, general linear model for repeated measurement data, Fisher exact tests for categorical variables, and Mann-Whitney U test for ordinal variables. All tests for statistical significance were determined using an alpha level of 0.05. All analyses were performed using SPSS 17.0.

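### The improvement claim rests on three unranked complications, each tested at 0.05 with no success rule, while the only quantified hypothesis is on feeding intolerance, which the plan merely observes

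*Protocol*

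**What the plan says.** **Protocol, Purpose.** Only the first purpose makes a comparative claim: "To investigate whether intermittent feeding with semi-solid nutrients improves the enteral nutrition complications of diarrhea, reflux and aspiration". It names three complications with no order among them. The second purpose is "Observe the feeding intolerance and the efficiency of the EN of critically ill patients" and the third is "Observe the blood sugar and insulin secretion". Neither makes a directional claim.

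**Protocol, Sample Size Calculating.** The design inputs rest on a different outcome: "the incidence of gastrointestinal intolerance (FI) is about 30.8" percent. With it come a margin of −0.05, alpha 0.025 and beta 0.20, and the text states that "the non-inferior efficiency test design is" adopted. None of the three complications in Purpose 1 has a rate, margin or effect size.

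**SAP.** The plan is one paragraph that assigns tests by type of variable, including "Fisher exact tests for categorical variables". It adds: "All tests for statistical significance were determined using an alpha level of 0.05". It names no primary analysis, testing order, multiplicity adjustment or success rule. Neither document calls any outcome primary or secondary.

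**The concern.** The outcomes that carry the claim and the outcome behind the design inputs are different, and nothing says which one decides the trial. There are two consequences.

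First, with three complications each tested at 0.05 and no rule for combining them, a report could claim improvement because any one of the three crossed the line. The chance of that happening by luck exceeds the chance for a single test.

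Second, a mixed result, such as less reflux with more diarrhea, has no pre-agreed reading as a verdict on Purpose 1. The same data could be presented as positive, negative or mixed, and the choice could be made after they are seen.

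This is separate from the mismatch between a non-inferiority design and difference tests. It would remain whichever kind of test were used.

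**Working it through.** The documents give no family-wise error rate, so there is no stated figure to reproduce.

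**Inputs from the documents.** Three complications (Purpose 1). Alpha 0.05 per test and Fisher's exact test (SAP); sidedness is not stated and is taken as two-sided. The rate 30.8% is given for FI only.

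**Assumptions.** Arm sizes of 30 to 200, and complication rates of 10% to 30.8%, equal in both arms. Outcomes are independent unless stated. Improvement is claimed if any one test is significant.

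**Step 1: nominal rate, either direction.** 1 − 0.95³ = 0.143 under independence. The upper bound under any dependence is 3 × 0.05 = 0.15.

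**Step 2: nominal rate, favourable direction only.** Half of each two-sided 0.05 favours the semi-solid feed, so 1 − 0.975³ = 0.073, with upper bound 3 × 0.025 = 0.075. The benchmark for one test is 0.025.

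**Step 3: correlation.** Simulation of three normal test statistics with a common assumed correlation:

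| Correlation | Either direction | Favourable only |
|---|---|---|
| 0 | 14.3% | 7.3% |
| 0.3 | 13.6% | 6.8% |
| 0.5 | 12.5% | 6.3% |
| 0.8 | 9.9% | 4.9% |

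**Step 4: Fisher's test.** It is conservative, so its true size is below 0.05. Exact enumeration gives the size s of one test. For three independent tests the rate is 1 − (1 − s₁)(1 − s₂)(1 − s₃). For example, at 100 per arm and 30.8%, s = 0.0348, so 1 − (1 − 0.0348)³ = 0.101. Counting favourable results only, s = 0.0174, which gives 0.051.

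| Per arm | Rates | Either direction | Favourable only |
|---|---|---|---|
| 50 | all 30.8% | 8.9% | 4.5% |
| 100 | all 30.8% | 10.1% | 5.1% |
| 200 | all 30.8% | 11.3% | 5.7% |
| 50 | 30/20/10% | 7.5% | 3.8% |
| 100 | 30/20/10% | 9.3% | 4.7% |
| 200 | 30/20/10% | 10.6% | 5.4% |
| 50 | all 10% | 5.3% | 2.7% |
| 30 | all 10% | 2.8% | 1.4% |

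The last two rows show that small arms with low rates remove most or all of the inflation.

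**Step 5: what a correction must cover.** Holm compares the smallest p-value with 0.05/3 = 0.0167, the next with 0.025 and the last with 0.05. If FI were tested at 0.05 and a separate Holm family also at 0.05, with no link between them, the joint rate could reach 1 − 0.95² = 0.0975. With FI at 0.025 it would be 1 − 0.975 × 0.95 = 0.074. The two must therefore be linked.

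**The case against.** **The one-hit rule is inferred.** Neither document says that one significant complication is enough. Purpose 1 can be read as three questions, each reported separately, and then a mixed pattern is simply reported. This stands in part. It rules out saying that Purpose 1 can have no answer, but the plan does not state this reading either, and the choice between readings is left open.

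**The direction matters.** A reader might infer that the false-positive rate for the improvement claim is far above 0.05. The documents do not support that. Chance harm is not chance improvement, and the favourable-only figures with Fisher's test are about 4–6%. The proper benchmark for them is 2.5%, so some inflation remains.

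**Independence is close to the worst case.** The adverse-event section of the protocol discusses reflux within its item on aspiration, so positive correlation between those two is plausible. This stands, and it lowers the figures.

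**Counting more outcomes.** A reader might add FI, glucose and C-peptide to reach 1 − 0.95⁶ = 26.5%. That is not a fair figure, because the plan only observes these outcomes and they cannot decide Purpose 1.

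**FI is not the only outcome with a hypothesis.** Purpose 1 is itself directional. FI is only the one with a quantified hypothesis.

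**Text may be missing.** The study-process section is empty in the available text, a figure is not shown, and the sample-size result may have been lost. Outcome detail could have stood there. However, the list of purposes and the SAP paragraph read as complete, and the SAP is where a hierarchy would be expected.

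**Conclusion.** The point holds in a moderate form. What depends on no assumption is that the plan has no primary outcome and no decision rule for its one comparative claim, and that its quantified hypothesis sits on an outcome it only observes.

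The size of the error inflation does depend on assumptions. If any one significant complication counts, the either-direction rate is at most 14–15% nominally. It is about 7–11% with Fisher's test at 50–200 per arm, for independent outcomes with rates all at 30.8% or spread over 30/20/10%. False improvement is about 4–6% against 2.5%, roughly double. Arm sizes and complication rates are not in the documents, and with small arms and uniformly low rates the inflation can vanish. The change should be made because it is cheap and removes a choice after the data are seen, not because the error rate is extreme.

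**What to change.** Amend the Purpose section and the SAP as follows.

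1. Name what is primary. There are two acceptable routes:
   - **FI as the single primary outcome**, since the design inputs rest on it. Define it, because the protocol calls it gastrointestinal intolerance in one place and feeding intolerance in another. Say whether it contains diarrhea or reflux, give its time window, and state one hypothesis type and alpha that match the sample-size section, with a matching analysis in the SAP. Test diarrhea, reflux and aspiration as key secondary outcomes only if FI succeeds.
   - **The three complications as the primary family**, with FI secondary. The sample-size section must then be aligned with that choice.
2. Under either route, apply Holm across the three complications at overall 0.05.
3. State that improvement is claimed for a complication only if its Holm-adjusted p-value is below 0.05 in the favourable direction. A mixed pattern is then reported complication by complication.
4. Label EN efficiency, glucose and C-peptide exploratory.

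**Cost.** The text changes are a few sentences, with no new data collection. The smallest of the three p-values must be below 0.0167. If FI is the gatekeeper and fails, the complications are not tested confirmatorily. Under the second route the sample-size calculation must be redone, and the number needed may change.

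### Exclusion 2, and exclusion 5 on its likely meaning, are realised durations under 3 days with no time origin; if randomisation is near ICU admission or EN start, applying them drops randomised patients

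*Protocol*

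**What the plan says.** All the relevant protocol text is in section 二, Design and method, except where noted.

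- Exclusion 2 in (3): "Stay in ICU less than 3 days".
- Exclusion 5 in (3): "No enteral nutrition received for less than 3 days".
- Exclusion 3, by contrast, states its timing: "acute pulmonary infection before entering the ICU".
- The abort criteria in (4) form a separate list, including "Abandoning treatment and discharge, resulting in incomplete data" and "EN contraindications nutrition during treatment".
- Under (5) Groups, "the treatment time for both groups is 3 days", and there is a stop rule: "If there were serious enteral nutrition complications such as aspiration and abdominal distension within 3 days, the experiment would end".
- Purpose 1 (section 一) asks whether the intervention "improves the enteral nutrition complications of diarrhea, reflux and aspiration". Purpose 2 covers feeding intolerance, whose literature rate of 30.8% drives the sample size formula in section 五.

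The SAP lists tests (Fisher's exact test for categorical variables) and an alpha of 0.05. It names no analysis set and no rule for excluded or stopped patients. The figure in (5) and the content of section 三 are not visible in the copy reviewed, so they may show when randomisation takes place.

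**The concern.** Exclusion 2 sets a threshold equal to the length of study treatment and words it as something that has happened. For a patient randomised on or soon after ICU admission, nobody can know on the day of allocation whether it is met. A site that follows the text would therefore remove the patient afterwards, because of discharge or death.

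Exclusion 5 is harder to read. Its likely meaning is EN received for less than 3 days, and on that meaning it has the same defect with a closer link to outcome. A patient whose EN is withheld on day 1 or 2 because of serious aspiration or distension would qualify for removal because of an event the trial sets out to compare. The arms differ in feed viscosity, which is meant to alter such complications, so unequal stop rates are plausible.

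At stake is whether the arms that are compared are still the arms that were randomised. No visible analysis-set rule would put removed patients back.

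**Working it through.** The plan gives no figure to reproduce here: no stop rate and no sample size are visible. The check is a reading of the text, followed by an illustration on assumed stop rates.

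**1. Reading.** Treatment lasts 3 days, and both criteria turn on fewer than 3 days. Exclusion 3 and abort criterion 2 each state when they apply; exclusions 2 and 5 do not. If randomisation falls at least 3 days after ICU admission and EN start, both are ordinary screening criteria and remove no randomised patient. If it falls near either start, the corresponding criterion is settled only after allocation.

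**2. Inputs.** From section 五: intolerance rate p = 0.308, margin 0.05, alpha 0.025, power 80%. Assumed: the share s of an arm whose serious distension ends EN before day 3 and who are then excluded, set at 1% in one arm and 2% or 3% in the other. IF is intermittent feeding; IS is the semi-solid arm.

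**3. Sample size for scale.** The protocol's formula with both rates 0.308:

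- alpha put literally into Z(1−alpha/2): n = (2.2414 + 0.8416)² × 2 × 0.308 × 0.692 / 0.05² = 1,621 per arm
- with Z = 1.96: 1,339 per arm

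**4. Shift in the intolerance difference.** Every excluded patient had an event, so the analysed rate is (p − s)/(1 − s):

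- s = 1%: 0.298/0.99 = 30.10%
- s = 2%: 0.288/0.98 = 29.39%
- s = 3%: 0.278/0.97 = 28.66%

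With no true difference, IS minus IF becomes −0.71 points (IF 1%, IS 2%) or −1.44 points (IF 1%, IS 3%). Swapping the arms gives +0.71 or +1.44. With equal s the difference is 0 and only the rates are understated. If IS is truly 5 points worse, equal s of 1% or 3% gives 5.05 or 5.15 points, which is almost no distortion.

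**5. Effect on a non-inferiority test.** P(non-inferior) = Φ((0.05 − diff)/SE − 2.2414), at 1,621 per arm before exclusion:

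| Stops (one arm v other) | True difference 0 | IS truly 5 points worse |
|---|---|---|
| none | 80.0% | 1.25% |
| 1% v 2%, IS stops more | 90.1% | 3.1% |
| 1% v 3%, IS stops more | 95.9% | 7.2% |
| 1% v 2%, IF stops more | 65.8% | 0.34% |
| 1% v 3%, IF stops more | 48.4% | 0.08% |

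At 1,339 per arm with Z = 1.96, the first column reads 80.0%, 89.4%, 95.2%, 67.3% and 51.7%.

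**6. Effect on the SAP's two-sided Fisher test at 0.05, no true difference.** In 4,000 simulated trials at 1,621 per arm, false significance was 4.7% with no exclusion, 6.9% at 1% v 2% and 13.5% at 1% v 3%. This depends strongly on sample size: at an assumed 100 per arm, a normal approximation gives about 5.1% and 5.6%.

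**7. Aspiration, taken separately.** The documents give no rate. For an assumed true rate of 5%, 10% or 20% in both arms, aspiration stops of 1% v 2% shift the difference by 0.98, 0.93 or 0.82 points; stops of 1% v 3% shift it by 1.98, 1.87 or 1.67 points.

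Steps 4 to 7 illustrate the exclusion 5 route. Early discharge or death under exclusion 2 need not be tied to these outcomes, and the documents give nothing from which to size it.

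**The case against.** The strongest reply is that these are screening criteria. The protocol separates exclusion from abort criteria; exclusions 1 and 3 are clearly pre-entry; and on-treatment contraindications and early discharge appear in the abort list. That makes a pre-entry reading possible, perhaps likely, but no visible text states it.

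Three further replies stand in part.

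- Exclusion 5 is a double negative. Taken literally it describes a gap of under 3 days without EN, which would suggest a pre-entry condition. Its post-randomisation effect depends on repairing the wording, so exclusion 2 carries the firmer part of the point.
- The stop rule in (5) ends the experiment, not necessarily EN. A patient who continues on routine EN can still reach 3 days and would not meet exclusion 5. An aspiration that triggers the stop has also been observed, and nothing says it goes uncounted.
- The illustration assumes every stop rate. It also holds total intolerance equal while serious distension differs two- or threefold.

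A reader might infer that the plan definitely removes randomised patients, or that it discards aspiration cases by design. The documents do not support either: the time of randomisation may be given in the missing figure or section 三, and that absence cannot be held against the plan.

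**Conclusion.** The point holds in conditional form. Exclusion 2 as written, and exclusion 5 on its likely meaning, would drop randomised patients for events after allocation if randomisation is near ICU admission or EN start. No visible rule prevents this. It is more than a missing detail, because following exclusion 2 to the letter would then break the randomised comparison.

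The size is not known. Under the assumed stops the intolerance difference moves by 0.7 to 1.4 points against a 5-point margin, in either direction, and by nothing if stops are equal. The error rates and power rest further on a sample size derived from the formula, not stated in the plan. A reader might infer a bias in favour of the semi-solid arm; the documents do not show which arm would stop more often. The change should be made. Confidence is medium, because the timing of randomisation is not visible.

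**What to change.** - Replace exclusions 2 and 5 with: *expected ICU stay and expected EN of at least 3 days, judged before randomisation*.
- Analyse all randomised patients in their assigned arm, including those stopped under (4) or (5).
- Count aspiration that stops feeding as aspiration, and serious distension that stops feeding as feeding intolerance.
- Tabulate stops by reason and arm.
- An analysis of patients completing 3 days may be added as a secondary sensitivity analysis only, with a note that it carries the same selection.

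The cost is a few lines in the protocol, SAP and case report form, and one table. The downside is that patients who leave early stay in the denominator with short follow-up, which dilutes differences and slightly favours non-inferiority. If 5% or 10% of each arm leave early with half their events observed (assumed), both rates are multiplied by 0.975 or 0.95. A true 5-point difference then becomes 4.88 or 4.75 points, and at 1,621 per arm false non-inferiority rises from 1.25% to 1.5% or 1.8%. If the sponsor already intends pre-entry screening, the rewording costs almost nothing.

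### A serious complication ends a patient's experiment, and nothing provides for recording or analysing the other outcomes afterwards, so their comparison may be biased

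*Protocol*

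**What the plan says.** Protocol section 二 (5), Groups, sets the treatment window ("the treatment time for both groups is 3 days") and what follows it ("After 3 days, you will receive routine enteral nutrition therapy"). Between randomisation and day 3 it adds a stopping rule: "If there were serious enteral nutrition complications such as aspiration and abdominal distension within 3 days, the experiment would end".

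Protocol section 一, Purpose, names the outcomes. The first aim is whether the semi-solid feed "improves the enteral nutrition complications of diarrhea, reflux and aspiration". The second is "Observe the feeding intolerance and the efficiency of the EN of critically ill patients" and the third is "Observe the blood sugar and insulin secretion". Aspiration is therefore both a study outcome and a named example of what ends the experiment.

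Incomplete data are mentioned once, in the abort criteria (section 二 (4)): "Abandoning treatment and discharge, resulting in incomplete data". No handling rule is attached. The SAP lists Fisher's exact test for categorical variables, t and Mann-Whitney tests, and a "general linear model for repeated measurement data". It names no analysis set, no missing-data rule, and nothing for unequal observation time or a competing event.

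**The concern.** The stop is a post-randomisation event tied to an outcome that the intervention is expected to change. If the hypothesis is right, the two arms stop at different rates. If recording ends at the stop, the time over which diarrhea, reflux, EN efficiency and glucose can be observed then differs by arm, for a reason connected with treatment.

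Neither obvious way of handling these patients is safe. Keeping them in the denominator treats a patient stopped on day 1 without diarrhea as diarrhea-free for three days. Excluding them breaks the randomised comparison. The usual repeated-measures general linear model drops any patient with a missing time point, so stopped patients would leave that analysis without an explicit decision. Observations not made during those days cannot be recovered later.

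**Working it through.** The plan states no stop rate, event count or final sample size, so there is no figure of its own to reproduce. The check asks how large a false difference the rule could create when the arms truly do not differ.

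**Inputs**
- Window: 3 days (Protocol section 二 (5)).
- True 3-day outcome risk: 30.8% in both arms. This is the feeding-intolerance rate in Protocol section 五, borrowed only as an illustration for diarrhea or reflux.
- Stop proportions s over 3 days: 5% to 30%. These are assumptions.

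**Case A: recording ends at the stop, and stopped patients without a prior event count as event-free.** With independent constant hazards:
- λd = −ln(1 − 0.308)/3 = 0.3682/3 = 0.1227 per day
- λs = −ln(1 − s)/3
- Recorded risk R(s) = λd/(λd + λs) × [1 − exp(−3(λd + λs))], where the exponential equals 0.692 × (1 − s)

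| s | 3λs | λd/(λd + λs) | 1 − 0.692(1 − s) | R(s) |
|---|---|---|---|---|
| 5% | 0.0513 | 0.8777 | 0.3426 | 30.1% |
| 10% | 0.1054 | 0.7775 | 0.3772 | 29.3% |
| 20% | 0.2231 | 0.6226 | 0.4464 | 27.8% |
| 30% | 0.3567 | 0.5079 | 0.5156 | 26.2% |

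False differences, with the arm with more stops looking better:
- 5% vs 10%: 0.7 points
- 10% vs 20%: 1.5 points
- 10% vs 30%: 3.1 points

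If the same patients are prone to both events, the gap widens. A simulated shared log-normal frailty with SD 1 gives about 2.3 to 2.4 points for 10% vs 20%, and 4.8 to 4.9 for 10% vs 30%.

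**Case B: stopped patients are excluded, 10% vs 20% stopped.** The correlated rows come from a gamma-frailty simulation with variance 1.
- Independent events: 30.8% in both arms, no bias.
- Positively correlated: 28.6% vs 26.2%; the arm with more stops looks better.
- Negatively correlated: 32.7% vs 34.8%; the arm with more stops looks worse.

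**Case C: mean glucose over observed time, 10% vs 20% stopped.** The difference (more stops minus fewer) is +0.04 mmol/L with an assumed trend of −0.5 mmol/L per day, 0 with no trend, and −0.04 with +0.5 per day. The sign follows a trend that the documents do not give.

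**Case D: recording continues to day 3 after the stop.** The truncation bias is zero.

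**The case against.** The strongest reply is that the protocol never says recording stops. The surrounding sentences concern feeding, so the rule may end only the assigned feed. The text available also lacks the figure under Groups, and section 三, Study process, is a bare heading, so a schedule may have been lost. This stands in part: non-recording is the ordinary reading of the rule, not stated text. But no passage available says that recording continues, and one sentence is needed under either reading.

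The rule is also limited to serious complications, while section 二 (6) separately tests pharyngeal and tracheal secretions. Aspiration as a measured outcome may be broader than the stopping event, so trigger and outcome may overlap only partly. That stands, and it could make stops rare. At assumed rates of 2% vs 5% the Case A difference is only 0.4 points.

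Four stronger conclusions are tempting, and the documents support none of them.
- **The arm with more stops must look better on diarrhea and reflux.** This requires stopped patients to be counted as event-free, which neither document says. Under exclusion the bias can vanish or change sign.
- **It must also look better on glucose.** Case C shows no fixed direction.
- **The rule could reverse a real benefit.** A calculation with no true effect cannot show that. With an assumed true 25.8% (semi-solid) vs 30.8%, the Case A formula gives 24.6% vs 27.8% at 10% vs 20% stopped, and 24.6% vs 26.2% at 10% vs 30%. The true 5.0 points shrink to 3.2 and 1.6 without reversing. The aspiration that triggers a stop is itself observed, so that benefit is not hidden by the stop.
- **The artefact can be measured against the plan's 5-point margin.** That margin and the 30.8% belong to feeding intolerance, which is undefined. If the stopping event counts as intolerance, those patients are recorded as events and that endpoint escapes this under-count.

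**Conclusion.** The concern holds as a possible bias of uncertain size, worth correcting. The protocol ends a patient's experiment at an outcome-related event that may differ by arm, and neither document says how the remaining outcomes are then recorded or analysed.

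The figures of 0.7 to 3.1 points apply only if recording ends, stopped patients count as event-free, the hazards are independent and constant, and the assumed stop rates and 30.8% risk are near the truth. Positive correlation between the events makes the figures larger, and rarer stops make them smaller. Under exclusion the sign depends on the correlation, and for glucose no direction can be given. The conclusion about the complete-case model rests on the usual behaviour of that procedure; the SAP specifies nothing else.

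**What to change.** Leave the clinical stopping rule as it is and separate it from data collection.

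- **Protocol section 二 (5):** state that the rule ends only the assigned feeding, and that diarrhea, reflux, aspiration, intolerance and blood sugar are recorded to the end of day 3 for every randomised patient still in the ICU.
- **SAP, binary outcomes:** analyse each as occurrence by day 3, in the arm assigned, whether or not the patient was stopped.
- **SAP, repeated measures:** replace the general linear model with a mixed model that uses all available values.

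The cost is up to about two more days of bedside recording in stopped patients, plus a few lines of text. The downside is that some off-treatment data enter the comparison, so it estimates the effect of assignment to a feeding method and not of three uninterrupted days on it.

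### The sizing formula halves α = 0.025 again (literally Z = 2.241), which matches no reading of the SAP's 0.05; sidedness is unstated and the SAP gives no non-inferiority rule

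*Protocol*

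**What the plan says.** The protocol's section 五 (Sample Size Calculating) takes a literature rate for FI: "the incidence of gastrointestinal intolerance (FI) is about 30.8" percent. It sets the margin with "We presume that $\delta = -0.05" and gives the remaining parameters as "\alpha = 0.025$, $\beta = 0.20$, the non-inferior efficiency test design is". The formula for the two equal groups has the multiplier "Z_{1-\alpha/2} + Z_{1-\beta})^2" and the variance term "\pi_1(1-\pi_1) + \pi_2(1-\pi_2", divided by the square of π1 − π2 − δ. The section does not say whether α is one-sided or two-sided, what value π2 takes, or which group is π1. No resulting n is legible after the formula.

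The SAP sets one level for everything: "All tests for statistical significance were determined using an alpha level of 0.05". It gives no side here either. For a binary outcome such as FI, the method it names is "Fisher exact tests for categorical variables". It mentions no non-inferiority test, margin or confidence interval.

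**The concern.** In a non-inferiority design, α = 0.025 is commonly a one-sided level, and its critical value is then taken at 1−α. A subscript of 1−α/2 belongs with a two-sided α, commonly 0.05. The protocol combines the first α with the second subscript, so anyone who applies the formula as printed uses a stricter critical value than either convention gives. The SAP's unsided 0.05 does not settle which was intended.

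At stake is whether a reader can tell which critical value produced the sample size, and at what level FI non-inferiority would be judged. The second question is more than notation: the trial is sized for a non-inferiority conclusion, but the SAP contains no procedure that would deliver one. Without a written rule, the level and the interval could be chosen after the results are seen.

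**Working it through.** **Inputs.** From the protocol's sample size section: α = 0.025, β = 0.20, δ = −0.05, equal groups, critical value at 1−α/2. From the SAP: level 0.05. Sidedness is stated in neither document. No n is legible, so there is no planned figure to reproduce.

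**Critical values.**
- Printed formula: Z(1 − 0.025/2) = Z(0.9875) = 2.2414, which is one-sided 0.0125 or two-sided 0.025.
- One-sided 0.025, or two-sided 0.05: Z(0.975) = 1.9600.
- One-sided 0.05: Z(0.95) = 1.6449.
- Power term: Z(0.80) = 0.8416.

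The SAP's 0.05 gives 1.9600 or 1.6449. Neither is 2.2414.

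**Effect on n.** For fixed π1, π2 and δ, the variance term and the denominator cancel in a ratio, so only (Z + 0.8416)² matters.
- Z = 2.2414: 3.0830² = 9.505
- Z = 1.9600: 2.8016² = 7.849
- Z = 1.6449: 2.4865² = 6.183

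The printed formula therefore asks for 9.505/7.849 = 1.211 times the n needed at Z = 1.960 (21% more), and 9.505/6.183 = 1.537 times the n needed at Z = 1.645 (54% more).

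**Power of a non-inferiority z-test at the printed formula's n.**
- Judged at 1.9600: Φ(3.0830 − 1.9600) = Φ(1.123) = 86.9%.
- Judged at 1.6449: Φ(3.0830 − 1.6449) = Φ(1.438) = 92.5%.

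**Reverse case.** This does not describe the printed formula. If two-sided 0.025 is intended but n was in fact computed with 1.9600, power at 2.2414 is Φ(2.8016 − 2.2414) = Φ(0.560) = 71.2%.

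**Dependence on the unknown rate.** Assume π1 = 0.308 and vary π2, which the text does not give. Per-group n under Z = 2.241 and Z = 1.960 is then:
- π2 = 0.208: 160 and 132
- π2 = 0.258: 385 and 318
- π2 = 0.308: 1621 and 1339
- π2 = 0.320: 2836 and 2342

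The ratio stays at about 1.21 throughout. The absolute n ranges so widely that none of these values can be attributed to the sponsor.

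**Which test.** All power figures above are for a z-test against the margin. Fisher's exact test has equality of the two groups as its null hypothesis and makes no use of δ, so these figures are not its power. A non-significant Fisher result would not show non-inferiority.

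**The case against.** The strongest defence is that the two α values need not conflict. One-sided 0.025 and two-sided 0.05 share the critical value 1.960, and one-sided 0.025 is a natural reading in a non-inferiority design. On that reading the only fault is the division by 2 in the subscript, and if the sponsor used 1.960 the practical effect is nil. The formula was also read here from text extracted from a PDF, in which the surrounding sentence is out of order, so the subscript should be checked against the sponsor's own file. All of this stands, and it limits the point to notation, sidedness and the missing decision rule. Even if the source file proved to have no division by 2, the unstated sidedness and the missing rule would remain.

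Two stronger readings are tempting and should be resisted. A reader might infer that the trial was over-sized by 21%. No planned n is legible, so nothing shows that 2.241 was used. A reader might also infer that analysing at 0.05 doubles the error rate set in the protocol. On the likeliest reading the levels are the same. In any case, the SAP attaches 0.05 to significance tests, with Fisher's test for categorical variables, and plans no non-inferiority test whose error rate could be compared with the protocol's.

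It is also fair to note that the protocol's Purpose section asks about improvement in diarrhea, reflux and aspiration, and lists feeding intolerance only as something to observe. The FI non-inferiority decision is implied by the sizing section alone, so correcting α would not by itself make that decision usable.

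**Conclusion.** The mismatch is real but minor. As printed, α = 0.025 with a 1−α/2 subscript gives Z = 2.241, and no reading of the SAP's 0.05 reproduces it. If 0.025 is one-sided, which is likeliest but unconfirmed, the SAP level agrees when read as two-sided, the subscript is wrong, and the error is conservative: about 21% more patients than needed, with 86.9% power instead of 80%. If 0.025 is two-sided, the formula is right for it and the SAP level is out of line. Confidence is high for the mismatch of notation and level only, not for its cause or its effect on the trial. The percentages assume a z-test against the margin; they do not depend on the event rates. Separately from the subscript, the SAP's named test for categorical variables cannot deliver the non-inferiority conclusion for which the trial is sized, at whatever level it is run.

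**What to change.** 1. State in the protocol whether α = 0.025 is one-sided or two-sided. If one-sided, write Z(1−α) with α = 0.025, or equivalently Z(1−α/2) with α = 0.05. If two-sided, keep the formula and carry two-sided 0.025 into the SAP for this comparison.
2. If FI non-inferiority is an intended conclusion, add to the SAP that it is judged by the confidence interval for the risk difference against the stated margin: two-sided 95% in the first case, two-sided 97.5% in the second.
3. Define the sign and direction of the margin, and say which group is π1. FI is an adverse outcome, and δ = −0.05 on π1 − π2 limits excess FI with semi-solid feeding only if π1 is the control group.
4. Restate n and power from the sponsor's own π1 and π2.

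The cost is low: one symbol or one α value in the protocol, a definition of the margin, and a sentence or two in the SAP. Whether the target n changes depends on which critical value the sponsor used, which the available text does not show.
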